6. INVESTIGATIONAL PLAN

6.1. Study Design

This dual-centre, randomized, controlled, investigator-blinded, comparative study will be conducted in 70 subjects (male and female subjects; age ≥ 2) with confirmed diagnosis of head lice infestation. All subjects will be randomized in a 1:1 ratio in both treatment groups.

In this study, a repeated treatment will be performed, as described in the literature. For two-treatment protocols, it is recommended that the second treatment should be applied on day 7 to day 8 and the final assessment should be on day 10 [15]. In total, 4 visits are planned:

- Visit 1 – Baseline visit (Day 0; first treatment)
- Visit 2 – Post treatment evaluation visit (Day 1: 24hrs +/- 3 hrs.)
- Visit 3 – 2nd treatment visit/evaluation (Day 7 + 1 day)
- Visit 4 – Final evaluation visit (Day 10 + 2 days)

Subjects complying with the in- and exclusion criteria will receive the study medication according to a subject number, allocated in ascending order in correspondence with their inclusion into the study. Both investigational products will be tested as described in the product leaflets in compliance with the above-mentioned treatment recommendations.

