8.2. Method of assigning volunteers to treatment groups / randomisation

Subjects who meet the inclusion criteria will be randomized to receive test product or reference product. Randomisation will be performed during the screening visit V1 on day 0. A block randomisation (block sizes of 2) will be performed by the external statistician using statistical software (R version 3.4.2; R development core team, 2017). The randomization schedule will be send to the sites prior to study conduct. All subjects will be enrolled into the study, sequentially beginning with Subject Number 1-70.

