10.4. Efficacy Analyses

Efficacy analyses will be performed on the ITT population, consisting of all subjects who were included and randomized in the study, with available baseline value of the primary endpoint and at least one follow-up visit for the efficacy parameters. All statistical test will be performed at a 5% level of significance.

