10.4.1. Analysis of primary objective

The cure rate (p) corresponds to the proportion of subjects who are cured at day 10 among all subjects that received any treatment at day 0. The aim of the study is to show superiority for the cure rate of the test product versus a predefined limit of 70%.

The following null hypothesis will be tested:

$$H_{0, \text{prim}}: p_T - p_R = 0 \text{ and } H_a: p_T - p_R > 15\%$$

A χ^2 -test of independence will be used to test the null hypothesis.

In case superiority could not be proven, non-inferiority will be tested. According to ICH guideline “Points to consider on switching between superiority and non-inferiority” [17], it is allowed to assess non-inferiority in to the absence of superiority. Prerequisites include:

- predefinition of a non-inferiority margin
- no correction in terms of multiplicity

As non-inferiority margin (δ), a 7.5% worse cure rate is regarded as clinically not relevant. The following null hypothesis will be used: $H_{0, \text{NI}}: p_T - p_R < \delta$, whereby $\delta = -7.5\%$. The lower, 95% confidence interval (CI) of the difference $p_T - p_R$ will be used for the test. If $H_{0, \text{NI}}$ will be rejected, non-inferiority cannot be shown.

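### Two centres are given one unstratified sequence of subject numbers and the between-arm test ignores centre, so precision can be lost if the centres differ in cure rate (minor)

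*Combined protocol and SAP*

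**What the plan says.** Section 6.1 describes the design: "This dual-centre, randomized, controlled, investigator-blinded, comparative study will be conducted in 70 subjects". It adds "All subjects will be randomized in a 1:1 ratio in both treatment groups", with subject numbers "allocated in ascending order in correspondence with their inclusion into the study".

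Section 8.2, repeated in substance in section 6.2, gives the method: "A block randomisation (block sizes of 2) will be performed by the external statistician using statistical software". It continues "The randomization schedule will be send to the sites prior to study conduct" and "All subjects will be enrolled into the study, sequentially beginning with Subject Number 1-70". No stratification factor, per-centre list, per-centre number range or central allocation step is described.

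For the comparison of arms, section 10.4.1 says that a chi-square "test of independence will be used to test the null hypothesis". Centre does not appear in section 10.4.1 or elsewhere in section 10. The significance level is given in section 10.4 ("All statistical test will be performed at a 5% level of significance"), without saying whether it is one- or two-sided.

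**The concern.** Two sites that enrol at the same time cannot both take the next number from one pre-distributed list without some shared counter, and none is described. If they do manage it, the two members of a block can fall in different centres. Blocking then balances the arms over the whole trial but not within each centre.

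Centre could matter. Application, combing and assessment are done by local staff, and the rationale in section 3 cites increasing resistance to classic insecticides. If cure rates differ by centre, a chance imbalance of arms between centres adds noise to the estimated difference, and the planned analysis has no step to remove it. What is at stake is the precision of the between-arm comparison: secondary objectives b and c in section 5.2, the basis of the sample size in sections 8.1 and 10.2, and the contrast that section 10.4.1 writes as the primary hypothesis.

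**Working it through.** **Inputs from the plan.** Two centres, 70 subjects, 1:1 (section 6.1); blocks of 2 (section 8.2); cure rates 95% v 55%, superiority margin 15 points, 80% power (sections 8.1 and 10.2); 5% level (section 10.4). **Assumed, because the plan gives neither:** the share of enrolment by centre and the cure rates by centre.

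**1. The plan's own sample size.** With unpooled variance and one-sided 5%:

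n = (1.645 + 0.842)² × (0.95×0.05 + 0.55×0.45) / (0.40 − 0.15)² = 6.185 × 0.295 / 0.0625 = 29.2, so 30 per arm.

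This reproduces section 10.2. With the 35 per arm of section 8.1, the standard error of the difference is √(0.295/35) = 0.0918, or 9.2 points. Power against the margin is Φ(0.25/0.0918 − 1.645) = 86.0% at one-sided 5%, and Φ(0.25/0.0918 − 1.96) = 77.7% at one-sided 2.5%.

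**2. Imbalance within a centre if the list is shared.** There are 35 blocks. At 50:50 enrolment in random order, a block is split between centres with probability 2 × 0.5 × 0.5 = 0.5. A split block adds +1 or −1 to the test-minus-reference count in a given centre. The variance is 35 × 0.5 = 17.5, so the SD is 4.2. Simulation agrees: the difference is 5 or more in 28% of trials and 6 or more in 18.7%. Other cases:

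- 70:30 enrolment: 35 × 0.42 = 14.7, SD 3.8.
- 80:20 enrolment: 35 × 0.32 = 11.2, SD 3.3.
- Consecutive groups of three (households, say) at the same site: SD 2.4, and 6 or more in 2.3% of trials.
- Contiguous number ranges for each site: difference at most 1.
- Separate blocked lists for each centre: SD 0.7.

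**3. Effect of one such imbalance.** Take a centre with 20 test and 15 reference subjects, the other centre with the reverse, and cure 20 points apart between centres. The estimated difference shifts by (20/35 − 15/35) × 20 = 2.9 points, in either direction by chance. The standard error is 9.2 points.

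**4. Power against the 15-point margin.** Simulation with 35 per arm, 50:50 enrolment and average rates at or near the plan's 95% v 55%, one-sided 2.5%:

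| Assumed cure by centre | Shared list, centre ignored | Shared list, stratified analysis | Per-centre lists, centre ignored | Per-centre lists, stratified analysis |
|---|---|---|---|---|
| No difference | 77.5% | 78.1% | 77.5% | 78.4% |
| Moderate: reference 45/65%, test 92/98% | 77.5% | 79.5% | 78.1% | 80.1% |
| Large: reference 35/75%, test 90/100% | 77.5% | 83.2% | 79.0% | 83.9% |

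At one-sided 5%, going from the first column to the last gives about 86.1% → 86.4%, 86.1% → 87.6% and 86.0% → 90.1%. The variance of the estimated difference falls by about 0%, 4% and 11%. A plain two-sided chi-square against zero difference has power 98.9–99.0% under the plan and 99.0–99.5% after both changes.

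**5. Type I error, two-sided 5%.** With a shared list the plain chi-square has size 4.8–4.9%, even with centres 40 points apart. With per-centre lists and the same unstratified test, size falls to about 4.4% with centres 20 points apart and to about 2.6% to 3% with 40. The Cochran-Mantel-Haenszel test stays at 4.8–4.9% with per-centre lists.

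**The case against.** The strongest reply is that little depends on this. The primary objective and endpoint in sections 5.1 and 5.3 compare the test-arm cure rate with a fixed 70%, and balance between arms plays no part in that. At the plan's rates the test that is actually named, a chi-square against no difference, has about 99% power either way. Centre gaps of 20 to 40 points have no support in the documents. Application by clinic personnel, staff training and the fixed combing routine of section 9.4.8 all narrow site differences. Nor do the documents say how the sites divide the list; contiguous ranges would hold the imbalance to 1, and household enrolment would reduce it. All of this stands, and it limits the size of the point.

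A reader might infer more than the text supports. One inference is that the comparison is biased or its type I error inflated; under a shared list neither is so, because the imbalance is random in direction and size stays just under 5%. Another is that precision is lost outright; with no centre effect the loss is essentially nil. A third is that a 2.9-point shift threatens the 7.5-point non-inferiority margin. That shift is one chance realisation, small beside a 9.2-point standard error, and non-inferiority is tested only if superiority is not shown.

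It is also fair to say that most of the gain comes from the stratified analysis and less from the lists. In the large scenario, stratifying the analysis alone gives 83.2% of the 83.9% reached with both changes.

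**Conclusion.** The point holds as a minor one. The documents give two centres a single number sequence without saying how the sites share it, and the comparison of arms leaves centre out. If the list is used in order of inclusion across both sites, which is the natural reading of section 6.1, arms can be unbalanced within a centre. Precision can then be lost if centres differ in cure rate.

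At one-sided 2.5% the recoverable power against the 15-point margin is about 2 to 3 points for the assumed moderate centre effect, about 6 for the large one, and under 1 with none. These figures rest on assumed centre cure rates and 50:50 enrolment in random order. The firm part is that the division of the list is unspecified and that a better method is available at almost no cost.

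**What to change.** In sections 6.2 and 8.2, state that a separate permuted-block list is generated for each centre, each with its own subject-number range. In section 10.4.1, compare arms with a Cochran-Mantel-Haenszel test stratified by centre, and report a Mantel-Haenszel (centre-stratified) risk difference with its confidence interval. Use the same estimate and interval for the superiority-margin and non-inferiority comparisons.

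Make both changes together, since centre-balanced lists with the unstratified chi-square make the test conservative.

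The cost is one run of the R randomisation program per centre and a sentence or two in section 10.4.1, with no extra subjects or visits. There are two downsides. A centre that stops mid-block may end one subject out of balance. And if blocks of 2 are kept, each site can work out every second allocation from its own previous one, so block size should be settled in the same change.

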8.3. Blinding

As both products are substantially different from each other in terms of packaging, smell and application method, it is not possible to do a double-blinded trial. Both, the subjects and the clinic personnel that will apply the investigational products, will be able to recognize the products. Therefore, an investigator-blinded study will be performed, and an independent assessor (investigator or study staff performing the assessments of hair and scalp, eyes, as well the efficacy and safety evaluations) will be blinded to the treatment. Appropriate measures will be taken to keep the assessor blind during the whole study. The assessor will not be involved in any procedure of the trial involving the handling, storage, and use of the products.

8.4. Removal of volunteers from treatment or assessment

8.4.1. Withdrawal criteria

- Serious Adverse Events (SAE's)
- Diseases requiring treatment that occur during the study, which do not constitute SAE's but which, in the opinion of the Principal Investigator, would probably prevent achievement of the study objectives.
- Non-adherence to the study conditions or relevant deviations from procedures as established in the study protocol.
- Withdrawal of consent.
- Duration of treatment < 15 minutes for test product or < 10 minutes for reference product.
- Severe irritation of the skin or the eyes on pre-treatment assessment on day 7.
- Use of any other anti-head lice therapy.

All details and reasons for removal of trial subjects from the study will be recorded in the study termination section of the Case Report Form (CRF). CRFs of all trial subjects entered into the study must be kept in the documentation of the study. Reasons for withdrawal of trial subjects will be entered into the final report of the study. Every effort must be made to follow-up trial subjects who terminate with drug-related AE's to determine the final outcome.

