6.4. Second Treatment (Day 7 + 1 day)

On study day 7 (+1 day), the scalp and hair will be examined for live head lice by blinded study staff. The life stage of the lice will be documented. The assessments of skin and eyes irritation will be performed within 1h prior to administration. Subjects without severe skin or eyes irritations will receive a second treatment with the assigned test product. The subjects will be asked for any concomitant medication taken during the study period and adverse events that occurred.

At visit 3 the following operations are being performed by the study team:

- Hair scalp assessment for living lice (all stages) by study staff (see chapter 9.4.8)
- Second application of the investigational products by the study staff
- Assessments of skin and eyes irritation, local tolerability
- Questioning on well-being
- Registration and documentation of any adverse events and/or changes regarding concomitant diseases, concomitant medication, withdrawal criteria
- Vital signs

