8.5. Intention-to-treat (ITT) and Safety population

The safety set/population consists of all subjects who were randomised and exposed to study medication.

The ITT population contains any subject included and randomized in the study, with available baseline value of the primary endpoint and at least one follow-up visit for the efficacy parameters.

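### Section 8.4.1 removes treated subjects from the study for short contact time, procedural deviations or severe Day 7 irritation, with no firm Day 10 assessment, no stated rule for a missing Day 10 result, and two efficacy denominators

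*Combined protocol and SAP*

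**What the plan says.** Randomisation takes place at Visit 1 on Day 0 (8.2). Three of the withdrawal criteria in 8.4.1 can only arise, or mainly arise, after that point:

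- "Duration of treatment < 15 minutes for test product or < 10 minutes for reference product"
- "Non-adherence to the study conditions or relevant deviations from procedures as established in the study protocol"
- "Severe irritation of the skin or the eyes on pre-treatment assessment on day 7"

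The 8.4 heading speaks of removal from treatment or from assessment. The operative sentence in 8.4.1 goes further: "All details and reasons for removal of trial subjects from the study will be recorded in the study termination section" of the CRF.

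On what follows, 8.4.2 asks for a post-study examination where one can be done, and places a drop-out's data other than adverse events in an appendix listing. Section 19.1 asks the investigator to make every effort to obtain a final evaluation, and also permits replacement. Sections 8.1 and 8.4.4 rule replacement out.

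On Day 7 irritation, 6.4 says: "Subjects without severe skin or eyes irritations will receive a second treatment with the assigned test product". It does not say what happens to the others at Day 10.

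On the analysis, 10.4.1 defines the cure rate as "the proportion of subjects who are cured at day 10 among all subjects that received any treatment at day 0". Section 8.5 limits the ITT population to randomised subjects "with available baseline value of the primary endpoint and at least one follow-up visit for the efficacy parameters", and 10.4 repeats the condition of "at least one follow-up visit for the efficacy parameters". Section 10.5 keeps subjects in the safety analysis whatever their treatment duration; 10.4 has no such sentence for efficacy. Section 6.5 calls a user of another pediculicide a treatment failure and then adds that no efficacy analysis will be done.

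**The concern.** Contact time, adherence to procedure and tolerability are consequences of treatment or of how it was delivered. Removing subjects on these grounds makes the group observed at Day 10 depend on events after randomisation. It is plausible, though not shown in the documents, that under-treated subjects are more likely to have live lice on Day 10. If such subjects drop out of the denominator, the observed cure rate rises.

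Two things are at stake. Day 10 outcomes, which are the primary endpoint, may be lost for subjects who could have been examined at a visit already on the schedule. And where an outcome is missing, the plan leaves it open whether the subject counts as not cured or does not count at all. With 35 subjects per arm, that choice should be made before any data are seen.

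**Working it through.** **Step 1: who is affected by which gap.**

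| Subject | 10.4.1 denominator | ITT in 8.5 and 10.4 | Gap |
|---|---|---|---|
| Short contact or deviation on Day 0, withdrawn, no later visit | In | Out | Two denominators |
| Same, but attends Day 1 | In | In | No stated rule for a missing Day 10 result |
| Removed at Day 7 for irritation, short contact or deviation, Day 1 attended | In | In | No stated rule for a missing Day 10 result |

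Section 6.5 defines cure as no living lice found at the final visit. Read with 10.4.1, this implies that a treated subject not shown to be cured is not cured, but no section says so outright.

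**Step 2: the plan's own figure.** Inputs from 10.2: 95% against 55%, margin 15%, power 80%, 5% level (sidedness not stated). With unpooled variance,

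n = (z₀.₉₅ + z₀.₈₀)² × [0.95×0.05 + 0.55×0.45] / (0.95 − 0.55 − 0.15)²

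= (1.645 + 0.842)² × 0.295 / 0.0625 = 29.2, so 30 per group.

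This reproduces the stated 30 at a one-sided 5% level. With the 35 per group of 8.1, the standard error is √(0.295/35) = 0.0918, and power is Φ(0.25/0.0918 − 1.645) = 86.0%.

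**Step 3: one subject in or out, against the 70% limit.** The plan names no one-sample test (10.4.1 names a χ² test of independence), so an exact one-sided binomial test at 5% is assumed. The number excluded is also an assumption. Take 29 cured in the test arm, with any excluded subject not cured:

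| Counted | Cure rate | p = P(X ≥ 29 given n, 0.70) |
|---|---|---|
| 35 (all treated) | 29/35 = 82.9% | 0.065 |
| 34 (one excluded) | 29/34 = 85.3% | 0.033 |
| 33 (two excluded) | 29/33 = 87.9% | 0.015 |

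One excluded subject changes the conclusion.

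**Step 4: false-claim rate at a true 70%.** The pass marks are 30/35, 29/34 and 28/33.

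| Excluded | Every excluded subject is a non-cure (upper bound) | Exclusion unrelated to outcome |
|---|---|---|
| 0 | 2.7% | 2.7% |
| 1 | P(X ≥ 29 of 35) = 6.5% | P(X ≥ 29 of 34) = 3.3% |
| 2 | P(X ≥ 28 of 35) = 13.3% | P(X ≥ 28 of 33) = 4.1% |

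At the planned true rate of 95%, exclusion hardly matters: the chance of a claim is 99.3% with none excluded and 99.4% to 99.8% with one.

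**Step 5: power cost of counting missing as not cured.**

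Against 70%, at a true 95% with pass mark 30 of 35, P(X ≥ 30 of 35 − m) is 99.3%, 97.4%, 91.9% and 78.6% for m = 0, 1, 2 and 3 missing in the test arm.

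Between arms, with margin 15%, one-sided 5% and 35 per arm, each affected arm's rate is multiplied by (35 − m)/35 and put into the Step 2 power formula:

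| m | Missing in each arm | Missing in test arm only |
|---|---|---|
| 0 | 86.0% | 86.0% |
| 1 | 80.2% | 75.5% |
| 2 | 74.2% | 63.2% |
| 3 | 68.1% | 50.5% |

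For m = 1 in both arms: rates 0.9229 and 0.5343, standard error 0.0956, Φ((0.3886 − 0.15)/0.0956 − 1.645) = 80.2%.

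**The case against.** The strongest reply is that little would be lost in practice. Site staff apply both products under supervision (7.4), and the only tolerated deviation is a longer contact time (7.5.1, 7.5.2), so short contact should be rare. That stands, and it limits the size of the point.

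Second, the final evaluation in 19.1 may well mean Visit 4, which 6.5 and 6.7 call the final evaluation. That is a fair reading, but 19.1 does not tie it to Day 10. That removal ends the scheduled visits is itself an inference, because the 8.4 heading leaves room for removal from treatment alone. The text supports either reading, which is why it needs settling.

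Third, requiring one follow-up visit is a common modified ITT choice, and 10.4.1 already has the fuller denominator. True, but the two sections govern the same analysis and differ.

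Four stronger readings are tempting and are not supported:

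- *That 6.4 contradicts 8.4.1.* Section 6.4 withholds the second application from subjects with severe irritation and is silent on their Day 10 follow-up. Both sections can be followed together.
- *That withdrawn subjects are excluded from the efficacy analysis.* Section 8.4.2 says their data are listed. It says neither that they are analysed nor that they are left out.
- *That the rule favours the test product over the reference.* Each arm has its own minimum contact time, and nothing in the documents shows which would lose more subjects.
- *That the false-claim rate would be 6.5% or 13.3%.* Those figures need every excluded subject to be a non-cure. If exclusion is unrelated to outcome, the rate stays below 5%.

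**Conclusion.** The point holds in a limited form and should be fixed. As written, the plan can lose Day 10 outcomes of randomised, treated subjects. It states no rule for a missing Day 10 result, and it gives two denominators for a subject withdrawn on Day 0 who has no later visit. Safety follow-up is not the gap: adverse events must be followed up in any case (6.5, 8.4.1, 8.4.2, 9.5.3.3). What may be lost after severe Day 7 irritation is the Day 10 lice count and the skin, eye and tolerability scores.

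The effect is probably small, and the documents give no frequency for these events. It matters mainly when the result lies near the 70% limit, as in Step 3, and hardly at all if the test product performs as planned. The figures against 70% rest on an assumed exact one-sided 5% test. Those between arms rest on a normal approximation at a one-sided 5% level, the level at which the plan's 30 per group reproduces.

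**What to change.** - **8.4.1:** make short contact time, procedural deviations and severe Day 7 irritation recorded treatment deviations. Severe Day 7 irritation omits the second application only. Keep these subjects on the scheduled visits to Day 10, as 6.3 already does for live lice on Day 1, and analyse them in the assigned arm.
- **8.5 and 10.4:** define the efficacy denominator as all randomised subjects treated at day 0, as in 10.4.1, whatever the contact time, and count a missing Day 10 result as not cured.
- **8.4.2:** state that drop-outs' efficacy data are analysed as well as listed.
- **6.5, the other-therapy criterion in 8.4.1, and 9.6:** count users of another pediculicide as failures throughout. Delete the remark in 6.5 that they are not analysed, and align the other two places.
- **19:** state that a withdrawal by the investigator stops treatment but not follow-up, where consent allows.
- **19.1:** delete the replacement sentence, which conflicts with 8.1 and 8.4.4.
- Optionally, add a per-protocol sensitivity analysis without short contact times.

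These are wording changes. Visits 2 to 4 are already scheduled, so no procedure is added. The price is a lower observed cure rate and, where Day 10 results stay missing, the loss of power in Step 5, which is largest if only the test arm loses subjects. Keeping subjects on the schedule to Day 10 is what limits that loss.
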